9.4.5 BASELINE DESCRIPTIVE STATISTICS

See 9.4.1

9.4.6 PLANNED INTERIM ANALYSES

NA

9.4.7 SUB-GROUP ANALYSES

NA

9.4.8 TABULATION OF INDIVIDUAL PARTICIPANT DATA

NA

9.4.9 EXPLORATORY ANALYSES

10 SUPPORTING DOCUMENTATION AND OPERATIONAL CONSIDERATIONS

10.1 REGULATORY, ETHICAL, AND STUDY OVERSIGHT CONSIDERATIONS

10.1.1 INFORMED CONSENT PROCESS

10.1.1.1 CONSENT/ASSENT AND OTHER INFORMATIONAL DOCUMENTS PROVIDED TO PARTICIPANTS

Consent forms describing details of the study intervention, study procedures, and risks will be given to the participant and written documentation of informed consent will be completed prior to starting the study intervention.

The following consent materials are submitted with this protocol:

- Participant informed consent
- Physician's consent
- Online screener
- Telephone screener

10.1.1.2 CONSENT PROCEDURES AND DOCUMENTATION

If the participant is deemed eligible and decides to participate, the participant will complete the consent form on-site or the study staff will send a link to the study participant to read and electronically sign the consent in REDCap.

All participants are required to obtain consent to participate from their Primary Care Provider.

10.1.2 STUDY DISCONTINUATION AND CLOSURE

This study has no pre-specified criteria for discontinuation or closure.

10.1.3 CONFIDENTIALITY AND PRIVACY

Assessment data will be collected and managed by study staff. Online data collection will be done through RedCap, and paper forms will be entered by study staff into a RedCap form. Data will be stored without identifiers. After all study activities are completed, data will be de-identified. Longitudinal measurements will undergo consistency and outlier checks, be compared with raw data, and edited as required. Audit trails will be used to document any database changes.

To ensure confidentiality of participants, all survey data and scale/tracker/dietary records related to a participant's involvement in this research study will be stored in encrypted files on servers that adhere to the University policy on storage and transmission of sensitive data. Participant identity on these records will be indicated by an ID number, and the information linking these numbers with participant identity will be kept separate from the research records. In addition, all research databases will have password-controlled access, and this will be controlled by critical staff.

All data records related to a participant's involvement in this research study will be stored in a locked file cabinet and/or in encrypted files on servers that adhere to the University policy on storage and transmission of sensitive data. Participant identity on these records will be indicated by an ID number, and the information linking these numbers with participant identity will be kept separate from the research records. In addition, all research databases will have password-controlled access, and this will be controlled by critical staff.

The Fitbit API will be used to access data from participants' scale, activity tracker, and Fitbit app. During the consent process, participants will consent for the data from their specific device IDs to be accessed by our study. They will need to enter their Fitbit username and password during the app setup process to allow Fitbit data to be sent to our study server. The study smartphone app uses a Standard Auth 2.0 security model for logging in to Fitbit. The study uses temporary access tokens that are stored only on the user's device and is not stored on our servers. Therefore, Fitbit usernames and passwords will not be stored in any way with this study. Instead, the weight and tracker data will be connected to participants by their unique study ID that they will also enter during the app setup process. Data are transmitted on secure servers that adhere to University policy on Sensitive Data. The risk of breach of confidentiality over the Fitbit websites will be partly subject to each individual's comfort in sharing information in their individual profile. To further minimize the risk of breach of confidentiality, all participant activities on the Fitbit websites will be voluntary. Consent forms will also clearly communicate the risk of this type of disclosure to participants

10.1.4 FUTURE USE OF STORED SPECIMENS AND DATA

Questionnaire data as well as physical measurements including height, weight, and HbA1c data collected for this study will be analyzed and stored on password-protected encrypted file servers at the University of North Carolina at Chapel Hill. No specimens will be stored.

10.1.6 SAFETY OVERSIGHT

Safety oversight will be under the direction of the Office of Human Research Ethics (OHRE) Biomedical IRB and the Principal Investigator.

10.1.7 CLINICAL MONITORING

NA

10.1.8 QUALITY ASSURANCE AND QUALITY CONTROL

Quality control (QC) procedures will be implemented as follows:

Informed consent --- Study staff will review both the documentation of the consenting process as well as all of the completed consent documents. This review will evaluate compliance with GCP, accuracy, and completeness.

Source documents and the electronic data --- Data will be initially captured on source documents (see **Section 10.1.9, Data Handling and Record Keeping**) and will ultimately be entered into the study database.

Intervention Fidelity — Consistent delivery of the study interventions will be monitored throughout the intervention phase of the study. Procedures for ensuring fidelity of intervention delivery are described in **Section 6.2.1, Interventionist Training and Tracking**.

Protocol Deviations – The study team will review protocol deviations on an ongoing basis and will implement corrective actions when the quantity or nature of deviations are deemed to be at a level of concern.

Should independent monitoring become necessary, the PI will provide direct access to all trial related sites, source data/documents, and reports for the purpose of monitoring and auditing by the sponsor/funding agency, and inspection by local and regulatory authorities.

10.1.9 DATA HANDLING AND RECORD KEEPING

10.1.9.1 DATA COLLECTION AND MANAGEMENT RESPONSIBILITIES

Data collection will be the responsibility of the clinical trial staff at the site under the supervision of the site investigator. The investigator will be responsible for ensuring the accuracy, completeness, legibility, and timeliness of the data reported.

Assessment data will be collected and managed by study staff. Online data collection will be done through RedCap, and paper forms will be entered by study staff into a RedCap form. Data will be stored without identifiers. After all study activities are completed, data will be de-identified. Longitudinal measurements will undergo consistency and outlier checks, be compared with raw data, and edited as required. Audit trails will be used to document any database changes.

To ensure confidentiality of participants, all survey data and scale/tracker/dietary records related to a participant's involvement in this research study will be stored in encrypted files on servers that adhere to the University policy on storage and transmission of sensitive data. Participant identity on these records will be indicated by an ID number, and the information linking these numbers with participant identity will be kept separate from the research records. In addition, all research databases will have password-controlled access, and this will be controlled by critical staff.

10.1.9.2 STUDY RECORDS RETENTION

Study documents will be retained until data analysis is completed. At this point, any materials with identifiers will be destroyed.

10.1.10 PROTOCOL DEVIATIONS

This protocol defines a protocol deviation as any noncompliance with the clinical trial protocol, International Council on Harmonisation Good Clinical Practice (ICH GCP). The noncompliance may be either on the part of the participant, the investigator, or the study site staff. As a result of deviations, corrective actions will be developed by the site and implemented promptly.

These practices are consistent with ICH GCP:

- Section 4.5 Compliance with Protocol, subsections 4.5.1, 4.5.2, and 4.5.3
- Section 5.1 Quality Assurance and Quality Control, subsection 5.1.1
- Section 5.20 Noncompliance, subsections 5.20.1, and 5.20.2.

It will be the responsibility of the site investigator to use continuous vigilance to identify and report deviations within 5 working days of identification of the protocol deviation, or within 5 working days of the scheduled protocol-required activity. Protocol deviations will be sent to the reviewing Institutional Review Board (IRB) per their policies. The site investigator will be responsible for knowing and adhering to the reviewing IRB requirements.

10.1.11 PUBLICATION AND DATA SHARING POLICY

NA

10.1.12 CONFLICT OF INTEREST POLICY

Any actual conflict of interest of persons who have a role in the design, conduct, analysis, publication, or any aspect of this trial will be disclosed and managed. Furthermore, persons who have a perceived

conflict of interest will be required to have such conflicts managed in a way that is appropriate to their participation in the design and conduct of this trial. The study leadership in conjunction with the University of North Carolina has established policies and procedures for all study group members to disclose all conflicts of interest and will establish a mechanism for the management of all reported dualities of interest.

10.2 ADDITIONAL CONSIDERATIONS

During the 12-week study, participants will monitor their blood glucose using the Abbott Freestyle Libre Continuous Glucose Monitoring system. For the CGM, a representative of the device manufacturer (Abbott) will train research staff to instruct study participants on the use of the device. The device is commercially available and measures blood sugar without the need for finger sticks. It involves placement of a sensor on the upper arm and use of a scanning device to "read" the sensor. Use of the device is considered 'off-label' for individuals without diabetes.

The study interventionists in this study are trained in behavioral weight control, have served this role in weight control interventions in the lab for 5 – 15 years, and are Master's or PhD level in Health Behavior, Nutrition (and Registered Dietitian), or Exercise Physiology.

10.3 ABBREVIATIONS

API	Application Programming Interface
BMI	Body Mass Index
CDC	Centers for Disease Control
CGM	Continuous Glucose Monitor
DPP	Diabetes Prevention Program
HbA1c	Glycated Hemoglobin
IRB	Institutional Review Board
NC TraCS	North Carolina Translational and Clinical Sciences Institute
OHRE	Office of Human Research Ethics
PAR-Q	Physical Activity Readiness Questionnaire
PHI	Protected Health Information
PI	Principal Investigator
REDCap	Research Electronic Data Capture

10.4 PROTOCOL AMENDMENT HISTORY

Version	Date	Description of Change	Brief Rationale
1	1/16/2019	Initial	NA
2	3/15/2020	In-person orientation, assessments,	COVID-19 restrictions

		counseling sessions suspended. Some final weights had to be done using remote weighing protocol (stepping on the Withings smart scale three times in a row, first thing in the morning).	
3	5/28/2020	Resume in-person assessments with the re-opening of the University effective June 1 for Human Subjects Research, following the guidelines of the Office of Research and the IRB. Transitioned to online consent to reduce the number of in-person visits necessary to conduct this study. We moved to conducting Orientation sessions via a Zoom call and send a link for the Informed Consent following the Orientation. The consent form will be deployed through REDCap and we will obtain an electronic signature. We will provide the study participant with a paper copy of the signed Informed Consent at the Baseline Assessment (which will take place in person).	COVID-19 restrictions

12 APPENDIX

Inclusion Criteria:

1. Currently age 20-65
2. BMI 25-50 kg/m²
3. Normal or impaired glucose as determined by HbA1c fingerstick (<6.5%)
4. Own an iPhone with a data and text messaging plan
5. Have home Wi-Fi access
6. Have the ability to read, write, and speak English
7. Not meeting the American College of Sports Medicine recommendation of 150 minutes of Moderate to Vigorous Physical Activity each week
8. Ability to attend weekly visits at the UNC Weight Research Program clinic for one month and weekly in-person, phone, or video call for an additional two months
9. Can obtain primary care provider consent that participation is appropriate

Exclusion Criteria:

1. Lost more than 10 pounds in the last 6 months
2. History of weight loss surgery
3. Currently participating in another physical activity or weight loss program or research study that may interfere with participation in this study
4. Currently meeting exercise recommendations of 150 minutes per week of moderate-to-vigorous physical activity
5. Currently pregnant, pregnant within the past 6 months, or planning to become pregnant within the next 4 months
6. Planning to relocate in the next 4 months

7. Pre-existing medical condition(s) that preclude adherence to an unsupervised exercise program, as determined by items endorsed on the PAR-Q (Physical Activity Readiness Questionnaire)
8. Diagnosis of diabetes
9. Taking medications to treat prediabetes
10. Report taking prescription or over the counter medication with a known impact on metabolism or weight
11. Current treatment for cancer
12. History of clinically diagnosed eating disorder
13. Diagnosis of schizophrenia or bipolar disorder
14. Hospitalization for a psychiatric diagnosis within the last year
15. Report a past diagnosis of or current symptoms of alcohol or substance dependence
16. Unwilling or unable to wear the CGM device continuously for the duration of the study
17. On dialysis

No exclusion criteria shall be based on race, ethnicity, or gender.

12.3 ONLINE SCREENER

Welcome to the T2 Connect Research Study screening questionnaire. These questions will take you approximately 5-10 minutes to complete. Once you complete the screener and submit your responses, you will be contacted by a study staff member by phone or by email. If you continue with the screening questions, your responses to the questions will be kept for the duration of the study for descriptive purposes.

Do you give your permission to continue with the online questionnaire and to be contacted by study staff if you are determined to be eligible for this study?

Yes No

- *If yes, continue screener*
- *If no, have message that says "Thank you for your interest in our program. If you wish to be informed of future studies, click here." Link to www.uncweightresearch.org/participate_cap.asp*

1. Do you read, write and speak English?

Yes No (INELIGIBLE)

2. How did you hear about this program?

- Facebook post (sponsored)
- Facebook post by friend, family, co-worker, etc.
- Tweet by friend, family, co-worker, etc.
- Email from friend, family, co-worker, etc.
- Website
- Listserv: If so, which one: _____
- Word of mouth (friend, relative, co-worker, etc.)
- Another study participant. Name _____
- Flyer
- Other (please specify): _____

3. What is your gender? Male Female

WOMEN ONLY COMPLETE THE NEXT 3 QUESTIONS

4. Are you currently pregnant or breastfeeding? Yes (INELIGIBLE) No

5. Have you been pregnant in the last 6 months? Yes (INELIGIBLE) No

6. Do you plan on becoming pregnant in the next 4 months? Yes (INELIGIBLE) No

7. What is your age? _____

break

The information gathered on this page is collected for descriptive purposes and does not influence your eligibility to participate.

8. Are you of Hispanic or Latino or origin?
 Yes No

9. Which race do you consider yourself to be? (you may choose more than one category):
 Black or African-American
 Asian
 American Indian or Alaska Native
 Hispanic, Latino, or Cape Verdean
 Native Hawaiian or Other Pacific Islander
 White
 Other (Specify): _____

break

10. What is your current weight? _____ lbs.

11. What is your height? _____ ft _____ inches

[BMI automatically calculated]

*The formula to calculate BMI is (weight in pounds * 703)/(height in inches * height in inches)*

12. Have you lost weight in the past 6 months?
 No Yes If yes, how much have you kept off? _____ lbs. (> 10 lbs = INELIGIBLE)

13. Have you ever had weight loss surgery?
 No Yes (INELIGIBLE)

14. In a typical week, how many days do you do any physical activity or exercise of at least moderate intensity, such as brisk walking, bicycling at a regular pace, and swimming at a regular pace?
 None
 1 day per week

- 2 days per week
- 3 days per week
- 4 days per week
- 5 days per week
- 6 days per week
- 7 days per week

15. On the days that you do any physical activity or exercise of at least moderate intensity, how long do you typically do these activities?

16. Have you ever had or are you currently receiving treatment for any of the following?

a. Pre-Diabetes or Diabetes Yes No (INELIGIBLE)

If yes, how is it controlled? _____

Diet and exercise

Prescription medication (INELIGIBLE)

Insulin (INELIGIBLE)

Other (describe)

b. Hospitalization in the past year for depression or other psychiatric disorder Yes (INELIGIBLE) No

c. Schizophrenia or bipolar disorder? Yes (INELIGIBLE) No

d. Alcohol or substance abuse? Yes (INELIGIBLE) No

e. Anorexia or bulimia? Yes (INELIGIBLE) No

f. Cancer Yes (Current treatment = INELIGIBLE) No

break

1. Has a doctor ever said that you have a heart condition AND that you should only do physical activity recommended by a doctor? No Yes (INELIGIBLE)
2. Do you feel pain in your chest when you do physical activity? No Yes (INELIGIBLE)
3. In the past month, have you had chest pain when you WERE NOT doing physical activity? No Yes (INELIGIBLE)

4. Do you ever lose your balance because of dizziness or do you ever lose consciousness?
 No Yes (INELIGIBLE)

5. Do you have a bone or joint problem that could be made worse by a change in your physical activity?
 No Yes

6. Is your doctor currently prescribing drugs for your blood pressure, cholesterol, or a heart condition?
 No Yes

7. Do you know of any other reason why you should NOT do physical activity?

NO YES

8. Are you currently on dialysis?

NO YES (INELIGIBLE)

9. Do you have an implanted medical device (for example, a pacemaker)?

NO YES (INELIGIBLE)

If yes, please describe: _____

Break

25. Are you taking any prescription medications?

NO Yes

26. Are you taking any non-prescription over the counter dietary supplements?

NO Yes

Break

27. Do you have access to the Internet at home? Yes No (INELIGIBLE)

If yes, How do you access the Internet at home (Check all that apply)?

- Computer (desktop or laptop)
- Smartphone or cell phone
- Tablet

If yes, do you connect to the Internet using home Wi-Fi, or another method such as mobile wireless (smartphone hotspot, USB key, etc.)?

- Home Wi-Fi (wireless connection) (INELIGIBLE if not selected)
- Smartphone hotspot
- Other (please specify): _____

28. What kind of smartphone or cell phone do you have (Check all that apply)?

- Traditional cell phone (not a smartphone)
- iPhone (INELIGIBLE if not selected)
- Android
- Other smartphone
- I do not have a cell phone or smartphone

29. (If iPhone) Do you have a data plan to access the Internet and receive text messages on your iPhone?

- Yes, unlimited
- Yes, but in limited amounts
- No, I only access the Internet on my smartphone when connected to Wi-Fi
- Other (please specify): _____

30. Are you planning on moving out of the area within the next 4 months?

- Yes (INELIGIBLE)
- No

31. Would you be willing to come for weekly study visits at the UNC Weight Research Program in Chapel Hill?

- Yes
- No (INELIGIBLE)

32. Thank you for completing these questions. In order to complete your eligibility screening, a study staff member will need to contact you by phone. Please enter your contact information below.

First Name:

Last Name:

Contact phone number:

Email address:

33. What is the best time to reach you (select all that apply)?

- Mornings
- Afternoons
- Evenings

34. If we call you to follow up about your eligibility, may we leave a message?

- Yes
- No

Please click "next" to complete the survey.

After Next, this message will appear: Thank you for completing the T2Connect research study screening questions. You will be contacted by a member of the study staff with information about your eligibility. Depending on the number of people interested in participating, it may take a few days for us to contact you. If you do not receive a call within 3-4 business days, please call our research center at [contact].

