5.2 EXCLUSION CRITERIA

An individual who meets any of the following criteria will be excluded from participation in this study:

- Lost more than 10 pounds in the last 6 months
- History of weight loss surgery
- Currently participating in another physical activity or weight loss program or research study that may interfere with participation in this study
- Currently meeting exercise recommendations of 150 minutes per week of moderate-to-vigorous physical activity
- Currently pregnant, pregnant within the past 6 months, or planning to become pregnant within the next 4 months
- Planning to relocate in the next 4 months
- Cannot attend weekly visits at the UNC Weight Research Program clinic
- Pre-existing medical condition(s) that preclude adherence to an unsupervised exercise program, as determined by items endorsed on the PAR-Q (Physical Activity Readiness Questionnaire)
- Treatment of diabetes with insulin or oral medications
- Report taking prescription or over the counter medication with a known impact on metabolism or weight
- Current treatment for cancer
- History of clinically diagnosed eating disorder
- Diagnosis of schizophrenia or bipolar disorder
- Hospitalization for a psychiatric diagnosis within the last year
- Report a past diagnosis of or current symptoms of alcohol or substance dependence
- Unwilling or unable to wear the CGM device continuously for the duration of the study
- On dialysis
- Have an implanted medical device such as a pacemaker

All participants will be required to obtain consent from their primary care provider in order to participate.

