8 STUDY ASSESSMENTS AND PROCEDURES

8.1 EFFICACY ASSESSMENTS

Note: Refer to the Schedule of Activities 1.3 for the timing and frequency of assessments.

Screening and Orientation

Screening, orientation, and enrollment procedures are described in section 5.5. At each point, study staff will confirm eligibility, as described. The participant has the choice to discontinue participation at any point. If participation is discontinued by staff or the participant, screening information will be held for the duration of the study and identifiers will be destroyed after the study is complete. Reasons for ineligibility will be retained for descriptive purposes.

Physical Measurements

Weight (kg) (primary outcome): Participants will be weighed wearing shorts and without shoes using a calibrated digital Tanita scale. Trained study staff will conduct these measurements following a standardized protocol. Two measures will be completed and the average of the two will be used. If the difference between the two measures exceeds 0.2 kg, a third measure will be taken.

Height (cm): Height will be measured at baseline using a wall-mounted stadiometer (Country Technology Inc, WI). Two measures of height will be taken and the average of the two will be used. If the two measures are not within 0.5 cm, a third measurement will be taken

BMI: Height and weight will be used to calculate BMI.

HbA1c will be measured with a fingerstick and analyzed on a point of care unit (Afinion Alere).

REDCap questionnaires:

Demographics. Participants will provide demographic information at baseline. They will provide age, gender, race/ethnicity, weight, and smoking history. (Baseline only)

Diabetes Specific Locus of Control.

We will administer an 18-item questionnaire consisting of three domains measuring diabetes-specific internal locus of control, powerful other locus of control, and chance locus of control (39).

Diabetes Obstacles Questionnaire. This is a diabetes-related quality of life questionnaire consisting of 30 items using a 5-point Likert-scale addressing social, psychological, cognitive, and behavioral obstacles (40).

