12.3 TELEPHONE SCREENER

1. When you filled out the online screening questions, you reported that your weight is _____ lbs. and your height is _____. Is this accurate to the best of your knowledge?

BMI = _____ **MUST BE 25 – 40;**

If BMI calc on edges of eligibility (25-27 or 38-40), “If you are eligible after we finish these screening questions and you decide you would like to participate, we will confirm your height and weight at your first study visit at our center.”

2. *If Yes to Cancer question 17.*

In the online screener, you reported having been diagnosed with cancer in the past. Can you tell me when that was? Are you currently being treated for Cancer? (If current treatment, INELIGIBLE)

3. *If yes to Question 23 on web screen: Do you know of any other reason why you should not do physical activity?*

In the online screener, you answered yes to the question “Do you know of any other reason why you should not do physical activity?” Can you explain? (INELIGIBLE if they can’t do activity akin to walking and progress to 150 minutes of Moderate to Vigorous PA per week over time)

4. *If Yes to Question 25 on web screen: Are you taking any other prescription medications?*

You reported that you are taking prescription medications. Can you tell me the names of them? (Also ask what it is used to treat)

If Yes, specify: _____

(NOTE: look for meds with known effects on appetite or weight, oral steroids, diabetes meds-- INELIGIBLE)

6. *If Yes to Question 26 on web screen: Are you taking any non-prescription over the counter dietary supplements?*

You reported that you are taking non-prescription over the counter dietary supplements. Can you tell me the names of them?

If yes, specify: _____

If other than vitamin/mineral supplement: Would you be willing to stop taking this supplement during the study period? **NO** (INELIGIBLE) Yes

7. Are you currently participating in any other weight loss or physical activity program?

8. Are you currently a member of any other research studies?

NO Yes

If yes, describe _____
(If other study would interfere with following study protocol, INELIGIBLE)

Thanks for taking the time to answer my questions.

You submitted the following contact information on the website (*read their info. from the web report*).
Has any of this changed? [*If so, note below*].

Name: _____

Street Address: _____

City: _____ State: _____ Zip Code: _____

Home Phone: _____ Work Phone: _____ Cell Phone: _____

Email Address: _____

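### The protocol excludes anyone ever diagnosed with an eating disorder, but the only screening question on the subject (online item 16e) names just anorexia and bulimia

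*Combined protocol and SAP*

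**What the plan says.** The exclusion appears twice. Section 5.2 lists "History of clinically diagnosed eating disorder", and exclusion 12 in the Appendix (Section 12) has the same words: "12. History of clinically diagnosed eating disorder". The two lists differ on some other criteria, such as the BMI range, but not on this one. Neither names particular eating disorders or makes an exception for any.

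The online screener (Section 12.3) introduces its health-history block with "Have you ever had or are you currently receiving treatment for any of the following". Part e of that block reads "e. Anorexia or bulimia". A Yes makes the applicant ineligible. There is no option for another eating disorder and no free-text field.

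The intervention that follows is set out in Section 6.1.1. Participants are encouraged to weigh themselves and record Red foods every day, and are taught to compare each day's weight with a goal. They are given a Red food limit meant to cut 500-1000 calories per day.

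**The concern.** A screening item should cover at least what its criterion covers. Here the criterion covers all diagnosed eating disorders and the item covers two. Someone diagnosed with, say, binge-eating disorder meets the exclusion and yet has an honest No to give at item 16e. Staff who follow the screener exactly can enroll a person whom the protocol says must not be enrolled.

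Two things are at stake. First, the exclusion is the only provision in the documents that deals with eating disorders. The risk discussion in Section 2.3.1 does not mention disordered eating, so no other safeguard specific to it stands behind the criterion. Second, a case recognized late could cost data. Section 7.2 lets the investigator discontinue a participant found to meet an exclusion criterion, and does not replace anyone who has already received the intervention. With 20 planned, each such loss is 1/20 = 5% of the sample.

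**Working it through.** The plan states no figure to reproduce on this point. The check sets the criterion beside each step that could apply it.

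1. **Scope of the criterion (Section 5.2; Appendix exclusion 12).** It covers any eating disorder, at any time in the past, provided it was clinically diagnosed. Both lists use this wording.

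2. **Scope of online item 16e.** The stem asks about ever having had the condition or being treated for it now, so lifetime history is covered. It also does not require a formal diagnosis, and in that respect reaches further than the criterion. The conditions, however, are limited to two. The gap is therefore in the list of conditions, not in the time window or the standard of evidence.

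3. **Neighboring items.** Item 16a has an open response for other means of control. Item 16b uses a catch-all: "Hospitalization in the past year for depression or other psychiatric disorder". Item 16e has neither. Item 16b does not fill the gap, because it needs a hospital admission within the past year.

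4. **Telephone screener (Section 12.3).** It covers BMI, cancer, reasons not to exercise, prescription drugs, supplements, and other programs or studies. It has no eating-disorder question. The nearest is the drug review, where staff ask what each drug treats and are told to "look for meds with known effects on appetite or weight, oral steroids, diabetes meds-- INELIGIBLE". A diagnosis could surface there, but only if the applicant takes a prescription drug for it.

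5. **Enrollment and baseline (Sections 5.5 and 8.1).** Height, weight, HbA1c and questionnaires are collected. The Personal Diabetes Questionnaire has a scale on eating problems, but it serves as an outcome and a counseling aid. No eligibility rule is attached to it, and it is not in the schedule table as supplied.

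6. **General eligibility check (Section 8.1).** The text says "At each point, study staff will confirm eligibility, as described". The only description it can refer to is the screening and enrollment process above, which contains no further question on this criterion.

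7. **Provider consent (Sections 5.1, 5.2, 10.1.1.2).** "All participants will be required to obtain consent from their primary care provider in order to participate". The physician's consent is listed in Section 10.1.1.1 as submitted with the protocol, but the form is not in the supplied text. Whether it asks about eating disorders is unknown.

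Count: two of two criteria lists use the broad wording; one screening item addresses the subject and names two diagnoses; no telephone or baseline item addresses the rest.

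**The case against.** The strongest reply is that an applicant who passes item 16e is not thereby certain to go unnoticed. The telephone screener asks what each prescribed drug is for. Item 16b stops anyone with a psychiatric admission in the past year. A primary care provider must agree to participation. Counseling is weekly and one-to-one, and Section 7.2 provides for discontinuing a participant who turns out to meet an exclusion criterion. This stands. A reader might infer that every other diagnosed eating disorder goes undetected, and the documents do not support that. They support only that no screening question shown asks about them directly. Nor can the provider form be counted as a gap, since it cannot be seen.

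A reader might also try to size the problem. If one assumes that 2% to 5% are affected, the chance of at least one among 20 is 1 - 0.98^20 = 0.33 to 1 - 0.95^20 = 0.64. The arithmetic is right but the input has no source in the documents. It would have to be the prevalence of diagnosed disorders other than the two named, and it would have to carry over from applicants to enrollees as if the indirect routes removed nobody. These percentages are not part of the conclusion.

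Finally, a reader might infer that such participants would respond differently on weight or food monitoring, or that the criterion exists to keep them from daily weighing and calorie restriction. Both are plausible. But the documents give no reason for the criterion and no evidence of a different response, and this is a single-arm pilot with no stated hypotheses (Section 9.1).

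What the reply does not do is close the mismatch. None of the indirect routes is described as checking eating-disorder history, and discontinuation comes after exposure has begun.

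**Conclusion.** The criterion and its screening item disagree, and the item is the narrower of the two in the conditions it covers. Followed as written, the screening questions shown can admit a person whom Sections 5.2 and 12 both exclude. This is an inconsistency that needs correcting, not merely a missing detail.

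Its size cannot be estimated from the documents. It does not call the trial's validity into question, and no effect on the primary endpoint is shown. The conclusion assumes that the supplied screeners are complete. If the provider consent form asks about eating-disorder history, the practical gap would be smaller, but item 16e would still not match the criterion.

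**What to change.** Reconcile item 16e with the stated criterion. Keep the existing stem and widen the item, for example: *e. Anorexia, bulimia, or any other diagnosed eating disorder (for example binge-eating disorder)? Yes (INELIGIBLE) / No*.

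The stem should stay. Replacing it with a question that asks only whether a health professional has made a diagnosis would cover more conditions, but would no longer stop people who report anorexia or bulimia without a formal diagnosis, whom the present item does stop.

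The cost is one reworded REDCap item and an IRB modification, with no new procedure or visit. Slightly more applicants will screen out.
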